### 6.3.6 End of Study and Follow-up

After the end of the study (i.e. at 61 weeks post-randomization), study participants will be asked to complete a close-out questionnaire via Hugo ([see Appendix 5](#)). They will also be asked at what health systems or clinicians from whom they received care over the past 61 weeks (including hospitalization, emergency department visit), to assess if all pertinent data were captured in the Hugo platform.

### 6.3.7 Removal of subjects

Discontinuation of the study intervention will be limited to voluntary patient discontinuation. Patient data will be monitored to watch for gaps in the device data of greater than 7 consecutive days, missed survey responses, as well as portal connection issues. Should an issue be noted, study staff will try to contact patients.

## 6.4 Statistical Method

### 6.4.1 Statistical Design

All analyses of results from this RCT will be conducted as intent-to-treat (ITT) to avoid the effects of crossover and dropout. We will report baseline descriptive statistics for the overall study, by site, and for both the control and treatment arms of the study. These will include patient age, sex, race, ethnicity and all co-morbidities, medical history and clinical characteristics. Baseline data will be compared using Pearson Chi Squared tests or Fisher exact test for dichotomous and/or categorical variables and student's t-tests for continuous variables. If variables are deemed as non-parametric, we will use a median test such as a Mann–Whitney *U*-test, where appropriate.

### 6.4.2 Sample Size Considerations

Analyses solving for minimum detectable effect sizes with 80% power were conducted with PASS software for only the primary outcomes (PASS 15). Because the models assume that each outcome is normally distributed, the outcome effects represent the average amount each outcome is expected to change with incremental shift in any explanatory variable. We will recruit a total of 100 participants and will randomly assign them to treatment and control arms based on a 50% probability of assignment. We also assume a 10% rate of drop-out between baseline and the end of follow-up, resulting in an effective sample size of N=80. Assuming a two-sided alpha threshold of 0.05, for the main outcome (change in ISI from baseline to 9-weeks post-randomization), and a power of 90% this sample size will allow us to detect an effect size of  $d=0.52$  which is  $\frac{1}{2}$  to  $\frac{1}{3}$  of what we have seen previously. Because this effect size is smaller than the levels demonstrated in randomized controlled trials, we are adequately powered to detect changes of interest in the main ISI outcome. We further note that this calculation is conservative because analysis may optionally draw from outcome values recorded at baseline and each follow-up time.

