## 5 Study Design

### 5.1 General Design Description

This will be a Phase 2 multi-center, randomized, controlled trial (2 group X 5 assessment design) whereby half of the patients with insomnia will receive the PEAR-003b digital therapeutic with linkage to Fitbit and half of the patients with insomnia will not receive the PDT, however will receive linkage to Fitbit (100 patients total: 50 at each site). The treatment duration will be 9 weeks and there will be a 21-, 35-, and 61-week follow-up. All patients will be evaluated at baseline, as well as prompted to complete additional assessments at weeks 9, 21, 35, and 61 weeks post randomization. The PEAR-003b intervention will deliver CBT-I via mobile devices as 6 treatment core modules over 9 weeks. Using the Hugo platform, we will also collect patient-generated engagement data, healthcare utilization, and patient activity/clinical outcomes for patients with insomnia.

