### 5.3.1 Number of Participants

We will enroll 50 patients at YNHH and 50 patients at the Mayo Clinic (100 total). Approximately 350 patients are anticipated to be screened at Yale.

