#### 6.1.3 Method of Assignment/Randomization (if applicable)

Patients will be randomized 1:1 to the digital therapeutic or the control arm by the RA using a randomization algorithm via Hugo. Patients will be notified if they are randomized to the treatment arm on day 14 by the RA and will be provided with instruction on how to set up and create their Pear-003b account if randomized to the Pear-003b arm. The study will not employ blinding as patients will need to know if they are completing the treatment

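### No blocking or stratification by site is stated, and the primary ISI model has no site term; the cost is probably small, but both are nearly free to add

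*Combined protocol and SAP*

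**What the plan says.** Section 5.1 sets the size as "100 patients total: 50 at each site" and says that "half of the patients with insomnia will receive the PEAR-003b digital therapeutic with linkage to Fitbit", the other half being controls. Section 5.3.1 repeats the figure of 50 per site.

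Two places describe allocation. Section 6.1.3 reads: "Patients will be randomized 1:1 to the digital therapeutic or the control arm by the RA using a randomization algorithm via Hugo". Section 6.4.2, on sample size, says the investigators "will randomly assign them to treatment and control arms based on a 50% probability of assignment". Neither says whether the algorithm uses blocks, stratifies by site or draws each patient separately, and neither describes concealment. Section 6.1.3 also says the study is not blinded.

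Section 6.4.3.1 gives the primary analysis of ISI change to 9 weeks as a 2 (group) × 2 (time) repeated-measures ANOVA and expects little confounding because the trial is randomized. Site is not in that model. Section 6.4.4 lists covariates without site and ties them to no model. Site is used only in the baseline descriptive tables (Sections 6.4.1 and 6.4.3.4).

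**The concern.** With two sites of 50, balance of arms within site is worth securing by design, and nothing in the plan says that it is. Section 5.3 describes different referral areas for the two centers, so site is a plausible prognostic factor. If it is prognostic for change in ISI, a chance imbalance moves the unadjusted difference in the trial actually run, and the difference between sites stays in the error term. If the algorithm does balance on site, leaving site out of the model wastes that balance. The stake is some precision in the primary comparison, and a reader's ability to see how allocation was done.

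**Working it through.** **Inputs.** 100 patients, 50 per site (Sections 5.1, 5.3.1); assignment probability 0.5 and ratio 1:1 (6.4.2, 6.1.3); effective N = 80, two-sided alpha 0.05, 90% power, d = 0.52 (6.4.2). Two inputs are assumptions: that 50% means an independent toss for each patient, and a site effect δ on ISI change, in units of the SD of change within arm and site. The documents give no δ, so a range is shown.

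**1. The plan's own figure.** The plan has no figure for balance. Its one related figure is the detectable effect, which does not reproduce. With 40 per arm, the normal approximation gives (1.960 + 1.282) × √(4/80) = 0.725, and the noncentral t gives 0.734, not 0.52. At d = 0.52 the power is about 63%. That is a separate fault. The losses below are taken at d = 0.73, where power at N = 80 is about 90%.

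**2. Overall split under a coin toss, X ~ Binomial(100, 0.5).**
- P(X = 50) = 0.080.
- P(55:45 or worse) = 0.368.
- P(60:40 or worse) = 0.057.
- A 60:40 split multiplies the variance by 1/(4 × 0.6 × 0.4) = 1.042. At N = 80 and d = 0.52, power goes from 63.2% to 61.4%; the effect detectable with 90% power goes from 0.734 to 0.749.

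**3. Split within a site, Binomial(50, 0.5).**
- P(30:20 or worse at a given site) = 0.2026.
- P(at either site) = 1 − (1 − 0.2026)² = 0.364.

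**4. Shift in the realised difference.** The share of patients from one site differs between arms with SD about √(0.25/50 + 0.25/50) = 0.10, so it stays within about 0.20 in 95% of trials. The shift is δ times that difference: at most 0.3 × 0.20 = 0.06 SD for δ = 0.3, and 0.5 × 0.20 = 0.10 SD for δ = 0.5. It averages zero over allocations.

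**5. Power and type I error.** In a 2 × 2 design the group-by-time test is the t test on change. With half the patients from each site and no site term, the variance of change is 1 + δ²/4.
- Simple assignment: the effective d is 0.73/√(1 + δ²/4). At δ = 1 this is 0.73/1.118 = 0.653.
- Stratified assignment: the error variance is overstated by the same factor, so the effective critical value is about 1.99 × √(1 + δ²/4). At δ = 1 this is 1.99 × 1.118 = 2.23, a type I error of about 2.9%.

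Simulation (N = 80, 20,000 trials per setting) gives:

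| δ (SD) | Power, simple, no site term | Power, simple, site term | Power, stratified, site term | Type I error, simple, no site term | Type I error, stratified, no site term |
|---|---|---|---|---|---|
| 0 | 89.7% | 89.3% | 89.8% | 4.9% | 5.1% |
| 0.3 | 89.0% | 89.3% | 89.8% | 4.9% | 4.9% |
| 0.5 | 87.9% | 89.3% | 89.8% | 4.8% | 4.5% |
| 1.0 | 81.9% | 89.3% | 89.8% | 5.0% | 2.9% |

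Against stratification with a site term, simple assignment without one loses 0.8, 1.9 and 7.9 points at δ = 0.3, 0.5 and 1. Against simple assignment with a site term it loses 0.3, 1.4 and 7.4.

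**The case against.** The strongest reply is that the plan may already do the right thing. A 50% probability is also each patient's marginal probability under 1:1 permuted blocks, so a reader who infers that the plan prescribes independent tosses, and so contradicts its own half-and-half split, goes beyond the text. This stands: the algorithm is unspecified, and steps 2 to 4 are conditional.

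Three other inferences also fail. Site totals cannot drift, because they are set at 50 each; only the arm split within a site can. A different standard of care by site is not documented: Section 6.3.5 names standard of care for controls without describing a site difference, and Section 6.3.4 gives all participants the same sleep-hygiene material. Nor is the primary test invalid: under simple assignment the type I error stays at about 5%, and chance imbalance is covered by the confidence interval.

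It is also fair that the analysis of change removes any stable difference in ISI level between sites, so only a difference in ISI change matters, and the documents show none. Simple randomization can be defended in an open-label trial because it cannot be predicted. Against that, randomly varying block sizes limit prediction, and Section 6.3.1 places randomization about two weeks after consent, so a guess at the next assignment has less scope to affect who is enrolled.

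What the reply does not meet is the missing site term, which helps under either reading of the algorithm.

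**Conclusion.** The point holds as a low-priority design improvement. The documents state no blocking or stratification by site and no site term in the primary model. If assignment is a coin toss, a split of 30:20 or worse in at least one site is fairly likely (36%), while a seriously uneven overall split is not (60:40 or worse in about 6%, costing under 2 power points). Omitting site costs about 0 to 2 power points at an assumed site effect of 0.3 to 0.5 SD on ISI change and about 8 at 1 SD. If the algorithm stratifies, omitting site makes the test conservative: about 4.5% at 0.5 SD and 2.9% at 1 SD. The size rests on the assumed site effect, on normally distributed change and on N = 80. No bias on average and no inflation of type I error follows.

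**What to change.** In Sections 6.1.3 and 6.4.2, replace the bare 50% statement with 1:1 permuted blocks of randomly varying size, stratified by site, run in the Hugo algorithm with upcoming assignments hidden from the research associate. If Hugo already works this way, say so.

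In Section 6.4.3, include site as a fixed factor, with its interaction with time, in the primary ISI model and in the secondary mixed models. The interaction is what adjusts the group-by-time comparison; a main effect of site alone adjusts only the level. The utilization t tests and the engagement correlations cannot take a model term and are outside this change unless they are replaced by models.

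The cost is an algorithm setting, a few sentences and one degree of freedom in the test of change, plus some predictability at block ends in an open-label trial, which the varying block sizes limit.

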### 4.2 Primary Objective

The primary objective of this study is to compare patient-reported outcomes of insomnia (ISI), collected through Hugo, as well as clinically validated metrics for insomnia, among patients randomized to receive PDT + Fitbit vs. Fitbit only at 9, 21, 35, and 61 weeks post-randomization.

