## 5.2 Outcome Variables

### 5.2.1 Primary Outcome Variables

The primary outcomes are a change in the ISI score from baseline to 9-weeks post randomization.

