### 6.4.3 Planned Analysis

#### 6.4.3.1 Primary Analyses

For the primary endpoint analysis, we will use a  $t$  test to compare the ISI scores for the intervention (PDT + Fitbit) and control group (Fitbit only) at baseline (as this score is a continuous variable). We will then use a 2 (group)  $\times$  2 (time) repeated measures analysis of variance (RM ANOVAs) to compare pre to post changes from baseline to 9-weeks across groups. Paired sample  $t$  tests by group will be used to examine time effects within each condition (if the overall interaction effect is significant). At weeks 21, 35, and 61 post randomization we will also perform the same analysis, but this will be as an exploratory secondary endpoint. If a patient drops out, we will carry forward the most recent patient-reported outcome measure response. As this is an RCT, we expect that confounding will be minimal. If patients are missing outcome data, we will use the last observation carried forward for the patient-reported outcome. Missing covariates will be set to missing.

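### The sample-size section claims a power margin from later ISI assessments, but the stated primary test uses only baseline and week 9, so the margin is unsupported

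*Combined protocol and SAP*

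**What the plan says.** Section 5.2.1 fixes the primary outcome: "The primary outcomes are a change in the ISI score from baseline to 9-weeks post randomization". Section 6.4.2 sizes the trial for that outcome: "Assuming a two-sided alpha threshold of 0.05, for the main outcome (change in ISI from baseline to 9-weeks post-randomization"; it then says that "a power of 90% this sample size will allow us to detect an effect size of" d = 0.52, with an effective N of 80. The section closes with the remark that "this calculation is conservative because analysis may optionally draw from outcome values recorded at baseline and each follow-up time".

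Section 6.4.3.1 specifies the primary test as a 2 (group) × 2 (time) "repeated measures analysis of variance (RM ANOVAs) to compare pre to post changes from baseline to 9-weeks across groups". On the later visits it says: "At weeks 21, 35, and 61 post randomization we will also perform the same analysis, but this will be as an exploratory secondary endpoint". Missing patient-reported outcomes are filled by last observation carried forward (6.4.3.1 and 6.4.5). A mixed model is planned for other outcomes in 6.4.3.2, but no multi-visit model is given for the ISI.

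The primary objective is wider than the primary outcome. Section 4.2 compares ISI "among patients randomized to receive PDT + Fitbit vs. Fitbit only at 9, 21, 35, and 61 weeks post-randomization", and the synopsis lists the same four time points.

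**The concern.** The closing remark of 6.4.2 credits the design with spare power from data that the named primary test does not use. A reader who accepts it will discount the risk of a false negative in a trial of 100 patients, and may overlook that d = 0.52 does not follow from the section's own inputs.

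There is a smaller, second issue. The remark calls the wider analysis optional, but no section says when the option would be taken or what status its result would have. Because the primary objective also lists all four time points, an analysis combining them could later be described as planned. It might answer a different question: an average effect over 61 weeks instead of the effect at week 9.

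**Working it through.** **Inputs.** From 6.4.2: effective N = 80 (40 per arm), two-sided alpha 0.05, 90% power, d = 0.52. From 6.4.3.1: group × time on two visits. The documents give no ISI SD and no correlation between visits, so every correlation ρ below is an assumption, shown over a range.

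**1. What the primary test is.** With two groups and two times, the group × time interaction is the two-sample t test on (week 9 − baseline). Its inputs are one change score per patient.

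**2. The plan's own figure.** Detectable d = (1.960 + 1.282) × √(2/40) = 3.242 × 0.2236 = 0.72 by the normal approximation, and 0.73 by the noncentral t. The stated 0.52 is not reproduced. Power at d = 0.52: 0.52/0.2236 = 2.326; 2.326 − 1.960 = 0.366; Φ(0.366) = 64%, or 63% by the t.

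Variants (two-sided 0.05, t-based):

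| Analysed | Detectable d, 90% power | Detectable d, 80% power | Power at 0.52 |
|---|---|---|---|
| 80 | 0.73 | 0.63 | 63% |
| 90 | 0.69 | 0.60 | 68% |
| 100 | 0.65 | 0.57 | 73% |

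The 90 row is 100 less the assumed 10% drop-out. The 80% column is included because the section opens with that power: "Analyses solving for minimum detectable effect sizes with 80% power were conducted with PASS software for only the primary outcomes". With 80 per arm (160 in total) the 90% figure is 0.516, which may explain the 0.52, but the documents do not say so.

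**3. What later visits add to the week-9 contrast.** In single-score SD units with 40 per arm, the variance of the between-group difference in change is 2 × 2(1 − ρ)/40 = 0.1(1 − ρ), that is 0.070, 0.050 and 0.030 at ρ = 0.3, 0.5 and 0.7. A five-visit unstructured model with complete data gives the same three values. The gain is zero. Missing week-9 values give no opening either, because carrying forward uses an earlier value, never a later one.

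**4. What baseline adds.** If d is in change-score SDs, baseline is already inside the outcome and no further gain is available from this test. If d is in single-score SDs, the detectable difference is 0.734 × √(2(1 − ρ)):

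| ρ (assumed) | 0.3 | 0.4 | 0.5 | 0.6 | 0.7 |
|---|---|---|---|---|---|
| Detectable, 40 per arm, 90% | 0.87 | 0.80 | 0.73 | 0.66 | 0.57 |

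Comparing week-9 scores alone would detect 0.73, so the change score gains only above ρ = 0.5. It reaches 0.52 at ρ of about 0.75, and at that point the baseline gain has been spent in reaching 0.52.

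**5. If an all-follow-up average could be substituted.** Take the second test as the mean of the four follow-ups minus baseline. Under compound symmetry its variance is 1.25(1 − ρ), that of the week-9 change is 2(1 − ρ), and their covariance is 1.25(1 − ρ). The correlation of the two tests is 1.25/√(2 × 1.25) = 0.79, whatever ρ is. The bivariate normal chance that at least one is significant at 0.05 under the null is 7.9%. With AR(1) correlations of 0.3 to 0.7 between successive visits, the tests correlate at 0.74 to 0.71 and the chance is 8.2% to 8.3%.

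**The case against.** Four points can be made for the plan.

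First, a reader might infer that a second primary analysis is open and that 0.05 is therefore not the true error rate. The documents do not support this. Section 5.2.1 fixes week 9, 6.4.2 names the same main outcome, and 6.4.3.1 names one test and makes the later weeks exploratory secondary. No section mentions averaging the follow-ups. An equally natural reading of the optional analysis is a longitudinal model with a week-9 contrast; with complete data and an unstructured covariance this has the same variance as the planned test, so choosing between the two would cause essentially no inflation. The 8% is conditional. What stands is that the wording does not rule a pooled analysis out.

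Second, a reader might infer that the planned test is anti-conservative when ρ is below 0.5. That holds only if d is in single-score SDs. The section powers the change itself, so change-score SDs are the more natural reading, and on that scale the detectable d does not depend on ρ.

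Third, some optional analyses would gain power. Adjusting for baseline by ANCOVA has a detectable difference of 0.734 × √((1 + ρ)/2) change-score SDs, or 0.59 to 0.68 for ρ of 0.3 to 0.7. Averaging four follow-ups would detect 0.734 × √(1.25/2) = 0.58 under compound symmetry if the effect were constant over time. Both are fair points about those analyses. Neither is the stated primary test, neither reaches 0.52 on this scale, and the second answers a different question.

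Fourth, the remark is an unquantified aside, and no stated N, d or power is said to depend on it. This stands, and it limits the weight of the point.

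**Conclusion.** The point holds as a correction to a stated property of the design. The calculation cannot be called conservative on the ground given: later visits contribute nothing to the stated primary test, and baseline is already in the outcome. On the section's own inputs, with d in change-score SDs, the detectable effect at 90% power is about 0.73, and power at 0.52 is about 63%. Even with all 100 patients analysed, the detectable effect is 0.65. These figures assume equal arms, normal change scores and a common variance. A gain from baseline under a single-score SD is possible but cannot be credited while ρ and the SD are unstated.

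The ambiguity about a pooled analysis is one of wording. Type I error of about 8% arises only if an all-follow-up average could take the place of the week-9 test, which the documents do not propose. The mismatches in 6.4.2 between 80% and 90% power, and between 10% drop-out and N = 80, are separate matters; they matter here because a claim of conservatism could lead a reader to dismiss them.

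**What to change.** - Delete the closing sentence of 6.4.2 that calls the calculation conservative.
- State in 6.4.2 that the power statement refers to the week-9 change comparison defined in 6.4.3.1.
- Add, in 6.4.2 or 6.4.3.1, that any ISI analysis pooling later follow-ups is secondary and cannot replace that comparison.
- If a gain from baseline is to be claimed, give the assumed baseline to week-9 correlation and say which SD d refers to.

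This takes a few sentences and changes neither the sample size nor the data collected. The cost is a power statement that reads slightly less favourably, and loss of the freedom to put a pooled analysis in the primary position.

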### 6.4.3 Planned Analysis

#### 6.4.3.1 Primary Analyses

For the primary endpoint analysis, we will use a  $t$  test to compare the ISI scores for the intervention (PDT + Fitbit) and control group (Fitbit only) at baseline (as this score is a continuous variable). We will then use a 2 (group)  $\times$  2 (time) repeated measures analysis of variance (RM ANOVAs) to compare pre to post changes from baseline to 9-weeks across groups. Paired sample  $t$  tests by group will be used to examine time effects within each condition (if the overall interaction effect is significant). At weeks 21, 35, and 61 post randomization we will also perform the same analysis, but this will be as an exploratory secondary endpoint. If a patient drops out, we will carry forward the most recent patient-reported outcome measure response. As this is an RCT, we expect that confounding will be minimal. If patients are missing outcome data, we will use the last observation carried forward for the patient-reported outcome. Missing covariates will be set to missing.

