Upon enrollment and following syncing of the Hugo and Fitbit devices (with assistance from the RA), patients in both study arms will complete a baseline assessment that will include questionnaires as well as 10 days of sleep diaries within a 14-day window. Questionnaires will relate to insomnia severity (ISI), depression (PHQ-8), daytime sleepiness (ESS), stress (PSS-10), health-related quality of life (SF-12) and anxiety (GAD-7). Please see **Appendix 2** for original paper versions of questionnaires. These PROMs will also be administered using the Hugo platform at 9-, 21-, 35-, and 61- weeks post-randomization. The RA will also ask patients to obtain credentials, if necessary, and connect portals to health systems where they receive care that are connected to Hugo but were unable to connect at enrollment. Patients will also receive a follow-up email from the RA that includes user guides for the Fitbit Inspire 2 (**see Appendix 3**). After the 14-day window, the patients will be randomized. Patients randomized to PEAR-003b will be contacted by the RA and will be guided through installing and initiating the CBT-I app.

The RA will collect the following data at enrollment:

- Number of people asked for study participation and number enrolled.
- Number of study participants who required assistance setting up YNHH portal.
- Number who had YNHH portal who could not be enrolled (e.g. because they had forgotten password, no space on mobile device, technical glitch, etc.).

If a patient refuses to participate, then we will note the number of people who refused. If the patient is agreeable, we will then administer a short questionnaire to understand their rationale for not participating in the study, to understand potential reasons for non-participation. We will also ask these people who chose not to participate about basic demographics, if they are willing to answer (age, sex, race/ethnicity, major co-morbidities, insurance status). Please see **Appendix 4** for questionnaire.

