### 6.3.5 On Study Visits

All patients will be asked to use the Hugo platform and Fitbit wearable for the entire 63-week period. Those randomized to PEAR-003b will be asked to complete the 6 core modules in 9 weeks, and at completion will be asked to fill out a questionnaire via Hugo to determine their satisfaction with the process of answering queries and will provide the opportunity for them to offer comments and suggestions for improvement. Patients will be asked to charge their Fitbit for the minimum necessary time during the day and try to wear it for as much time as possible. We will cycle patient reminders about charging the Fitbit for continuous study use based on the anticipated battery life of the Fitbit wearable. Based on our prior experience conducting both SHUTi and Hugo projects, we anticipate being able to stream electronic health record and patient-generated data from the Fitbit into our researcher database using the Hugo platform. The enrollment visit is the only time patients will need to come in for an in-person visit. All subsequent visits will be completed at home. For all patient-reported outcome measures, we will query patients regarding whether they prefer a secure email link or text message link to receive questionnaires at baseline, 9, 21, 35, and 61 weeks. If patients do not respond to this prompt within 24 hours, they will receive an email reminder. Should there be still be no response after an additional 48 hours, the RA will follow up with the patient via phone to ask the patient to complete the unanswered survey.

Patients will be contacted by the RA via phone at 35 and 61 weeks to ascertain any new health systems in which they sought care and the Hugo platform will be checked to ensure that data from those health systems are included (and patients will be asked to link those health systems or provide data, as appropriate). Multiple attempts will be made to contact patients if they are not contacted on the first attempt. Patients will receive automatic reminders to complete questionnaires at 9, 21, 35, and 61 weeks post-randomization via email. Similarly, patients will receive automatic reminders to sync their Fitbit at these time points.

- **Enrollment Visit (in-person) [~3 hours total]:**
  - Informed Consent/study enrollment
  - Fitbit setup
  - Hugo account setup
  - Baseline Surveys: Baseline Questionnaire; ISI; PHQ-8; GAD-7; ESS; PSS-10; SF-12
  - Begin sleep diaries
- **Day 15 post-enrollment**

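### The primary ISI test is a t test on change that fixes the baseline slope at 1; adjusting for the baseline ISI already collected would usually be more precise at almost no cost

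*Combined protocol and SAP*

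**What the plan says.** Section 5.2.1 defines the endpoint: "The primary outcomes are a change in the ISI score from baseline to 9-weeks post randomization". Section 6.4.3.1 analyses it in two steps. A t test first compares ISI "for the intervention (PDT + Fitbit) and control group (Fitbit only) at baseline". A 2 (group) × 2 (time) model follows, described as "repeated measures analysis of variance (RM ANOVAs) to compare pre to post changes from baseline to 9-weeks across groups". Paired t tests within each arm come last, "if the overall interaction effect is significant", so the group-by-time interaction is the decisive test. Missing ISI is filled by last observation carried forward (LOCF).

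Baseline ISI is available to every analysis. Section 6.3.5 lists it at the enrollment visit ("Baseline Surveys: Baseline Questionnaire; ISI; PHQ-8; GAD-7; ESS; PSS-10; SF-12"), and section 6.3.4 puts it before allocation: "patients in both study arms will complete a baseline assessment that will include questionnaires", and then "After the 14-day window, the patients will be randomized". Section 6.1.3 gives 1:1 allocation.

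No section specifies a baseline-adjusted model for the primary outcome. Section 6.4.4 gives an open-ended list of covariates that does not name baseline ISI and is tied to no model. Section 6.4.2 says only that the "analysis may optionally draw from outcome values recorded at baseline and each follow-up time". The mixed model in section 6.4.3.2 is for secondary and exploratory outcomes.

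**The concern.** An interaction test in a 2 × 2 repeated-measures layout uses the baseline score in one way only: it subtracts it in full. That is the best use only if week-9 ISI rises one point for each extra point at baseline. If the true slope is below 1, subtraction overcorrects. It adds noise, and a chance difference between arms at baseline passes into the treatment estimate through regression to the mean. The planned t test at baseline does not change the estimate, so it cannot repair this.

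The sample is fixed at 100 patients. At stake are the width of the confidence interval for the main result and, if the true effect is near the plan's detectable effect, the power. The validity of the test is not in question.

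**Working it through.** **Inputs from the documents.** N = 100, 1:1; two-sided alpha 0.05; drop-out 10%; stated effective N = 80; d = 0.52 at 90% power; earlier effects two to three times as large (all section 6.4.2 except the ratio, section 6.1.3). The scale of d is not stated.

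**Assumed, because the documents do not give them.** ρ, the correlation of baseline with week-9 ISI, and k, the week-9 SD divided by the baseline SD. Ranges shown: ρ 0.3 to 0.7, k 0.8 to 1.5.

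**The plan's own figure.** A two-sided two-sample t test with 40 per arm and d = 0.52 has 63% power, not 90%. The detectable d is 0.73 at 90% power and 0.63 at 80%. This is a separate problem, and nothing below depends on it. It does mean that precision is not ample at the plan's detectable effect. Since 10% drop-out from 100 leaves 90, N = 90 is used below, with N = 80 and 100 as checks.

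**Step 1: identity.** With two arms, two times and complete pairs, the interaction F equals the square of the t statistic on change. On simulated data both were 15.1384. LOCF completes the pairs, so the identity holds for the planned data set.

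**Step 2: variance.** Per patient, in units of baseline variance:
- change score: 1 + k² − 2kρ
- ANCOVA: k²(1 − ρ²)
- difference: (1 − kρ)², which is never negative and is zero only when the slope kρ equals 1.

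Under 1:1 allocation this large-sample ordering holds even if the slopes differ by arm. The ratio of ANCOVA to change-score variance is k²(1 − ρ²)/(1 + k² − 2kρ):

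| k | ρ = 0.3 | ρ = 0.5 | ρ = 0.7 |
|---|---|---|---|
| 0.8 | 0.502 | 0.571 | 0.628 |
| 1.0 | 0.650 | 0.750 | 0.850 |
| 1.3 | 0.805 | 0.912 | 0.991 |
| 1.5 | 0.871 | 0.964 | 0.998 |

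The interval narrows by 1 − √ratio. For k = 1 that is 19%, 13% and 8%. At ρ = 0.5 it is 24% for k = 0.8 and 4.5% for k = 1.3.

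**Step 3: finite-sample cost.** Estimating the slope inflates the variance by 1 + 1/(N − 4), which is 1 + 1/86 = 1.012 at N = 90. In 20,000 simulated trials of 40 per arm with a true slope of exactly 1, the ratio was 1.012. With equal SDs and no treatment effect, both tests rejected about 5% of the time and both estimators were unbiased.

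**Step 4: power at N = 90, d = 0.52** (noncentral t; ANCOVA with N − 3 df and the inflation above):

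| ρ, k | d per SD of change: planned → ANCOVA | d per baseline SD: planned → ANCOVA |
|---|---|---|
| 0.3, 1 | 68% → 85% | 54% → 72% |
| 0.5, 1 | 68% → 80% | 68% → 80% |
| 0.7, 1 | 68% → 75% | 88% → 92% |
| 0.5, 1.3 | 68% → 72% | 54% → 58% |
| 0.7, 1.3 | 68% → 68% | 74% → 74% |

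For d per SD of change and k = 1, N = 80 gives 63% → 81%, 75%, 70%, and N = 100 gives 73% → 89%, 84%, 79%.

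At the smaller earlier effect, 2 × 0.52 = 1.04 SDs of change, the planned test already has 99.6% power at N = 80.

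**Step 5: LOCF.** All 100 patients were kept, and a random 10% had baseline carried forward to week 9 (6,000 simulated trials). The ratios are 0.69, 0.78 and 0.88 for k = 1, and 0.92 for ρ = 0.5, k = 1.3. The gain is slightly smaller but remains.

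**Step 6: chance imbalance.** With 50 per arm, the standard error of the baseline difference is √(4/100) = 0.20 baseline SD. An imbalance of that size shifts the change-score estimate by 0.20(1 − kρ): 0.14, 0.10 and 0.06 baseline SD at ρ = 0.3, 0.5 and 0.7 with k = 1.

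**The case against.** The strongest reply is that nothing here is an error. The endpoint is change in ISI, the planned test addresses change directly, it is valid under randomisation, and the plan cites earlier work for it. If the true effect is as large as section 6.4.2 reports from earlier experience, power is above 99% either way. The gain rests on two unknown quantities and can be close to nothing.

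Most of this is true and limits the point. It is an efficiency improvement, and at large effects only the interval narrows. The gain vanishes as kρ approaches 1, which needs a week-9 spread well above the baseline spread or a very high correlation.

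Three things remain. The endpoint does not conflict with ANCOVA: with baseline ISI in the model, the arm contrast is the same whether the outcome is week-9 ISI or change. The trade is lopsided, at most about 1% of variance lost against up to half saved on the grid above. And section 6.4.2 calls its calculation conservative because baseline values may optionally be used, so naming the model closes a choice that would otherwise be open in an unblinded trial.

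One limit on the benefit: ANCOVA removes only the part of a chance imbalance that is linearly related to baseline ISI.

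**Conclusion.** The point holds. The primary test is the t test on change in ISI. It is valid, and under 1:1 allocation it is in large samples never more precise than ANCOVA on a score that is already collected before randomisation. With equal SDs and ρ from 0.3 to 0.7, the variance falls by 35% to 15% and the interval by 19% to 8%. Over the wider grid the variance ratio runs from 0.50 to almost 1. Every size given here rests on assumed ρ and k, and the power figures also depend on how d is scaled. The change is worth making because it costs almost nothing, not because the planned test misleads. LOCF affects both analyses and is a separate matter: where baseline is carried forward, it sets change to zero.

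**What to change.** In section 6.4.3.1, replace the 2 × 2 repeated-measures ANOVA with an ANCOVA of week-9 ISI on arm and baseline ISI. Report the adjusted mean difference with its 95% confidence interval. Remove the baseline t test from the primary analysis. Use the same model at weeks 21, 35 and 61. Site may be added as one further term for the two-centre design; no gain in precision is claimed for it. In section 6.4.2, replace the optional use of baseline values with a reference to this model.

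If LOCF is dropped, the week-9 contrast from a mixed model with baseline ISI as a covariate serves the same purpose. The two handle missing week-9 scores differently, so one should be named in advance as primary.

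The cost is one degree of freedom (two with site) and no new data, patients or procedures. Section 7.2 requires an approved IRB amendment for any protocol change. Because the trial is unblinded, the amendment should be fixed before anyone examines ISI outcomes by arm.
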